The CLOSE study¹⁵ analyzed the utility of AI for the reduction of AF recurrences with 91.3% of the patients free from AF/AT/atrial flutter (AFL) at 12 months follow-up. The CLOSE protocol targeted an inter-lesion distance of 6 mm and AI \geq 400 at the posterior wall and \geq 550 at the anterior wall. Nonetheless, in over 40% of patients, the target AI of 400 was not attained on the posterior wall owing to chest pain and/or intraesophageal temperature rise (IQR: 378–425 AU). The same 550 and 400 AI target values were used in a retrospective study comparing AI vs. CF-guided ablation resulting in significantly lower AT/AF recurrences on the AI arm.¹³ Such targets were chosen based on a previous study that retrospectively analyzed the ablation settings at first AF ablation of patients having redo ablation. Mean AI and mean FTI being statistically lower for reconnected segments [mean AI: 395 (350–429) vs. 422 (380–464), $p=0.002$; mean FTI: 311 (225–373) vs. 371 (260–502) gs, $p=0.003$].¹²

The left atrial wall is a thin structure with heterogeneous thickness, ranging from < 1mm to > 5 mm, with an important inter and intra-patient variability.¹⁶ This variability in wall thickness is the result of a complex array of three-dimensional muscular strands.¹⁷⁻¹⁹ A prospective study already showed that first pass PVI was limited by inability to create

transmural lesions in certain anatomical sites where left atrial wall thickness (LAWT) had been described as being higher in ex-vivo hearts.^{18,20} LAWT was an independent predictor of reconnection,²¹ dormant conduction²² and AF recurrence after 12 months follow-up,²³ and it might even be a predictor of transition from paroxysmal to chronic AF.²⁴

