The relationship between FTI and AI values, LAWT and gap formation on the ablation line after PAF ablation was already studied in two small retrospective studies that used single-point LAWT measurements. Nevertheless, the anatomical location of the measured points in the multidetector cardiac tomography (MDCT) may have not corresponded exactly to the real-time catheter position as seen with the CARTO Merge® (Biosense Webster, Diamond Bar, CA, USA) module. These studies showed that FTI/wall thickness and AI/wall thickness indexes have demonstrated to predict gaps on PVI lines.²⁵ Although this relationship might also be explained by the fact that the anatomical regions where tissue is thickest are also regions where catheter stability is more difficult to obtain. Therefore, AI is the most suitable index to look at since it also takes stability on account.

Even though many limitations have been described on MDCT atrial wall thickness measurement for previous generations of scanners, modern machines allow for sub-millimetric resolution. In fact, MDCT-derived LAWT measurements have been reliably validated on a porcine model.²⁶ 3D LAWT maps have already been generated from contrast-enhanced MDCT images,²⁷ although their integration on a 3D anatomical mapping system for clinical use has not been described yet.

Of all the determinants of lesion creation, LAWT is one key element that has been evaluated in some retrospective analysis but is not yet used as per procedure to dose the radiofrequency delivery. Adapting AI to local LAWT would be very useful in standardizing the ablation procedure with parameters fitted to each patient, enabling the development of a personalized approach that will both: i) increase efficacy by performing transmural lesions to prevent the formation of conduction gaps in the initial lesion set, and ii) increase safety by preventing excessive RF delivery on thin wall areas which can lead to complications, like cardiac perforation or atrio-esophageal fistula.

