complete a RF circle around the PV ostia (nephroid shape) on the 3-dimensional geometry using a Thermocool SmartTouch 3.5-mm irrigated tip contact force-sensing RF ablation catheter (Biosense Webster, Inc.). In case of a common ipsilateral vein ostium, the line must be drawn around the trunk. PVI will be started in all cases at the right PVs; PV isolation initiated from the right anterior ganglionated plexi (located at the supero-anterior area of the RSPV antrum) could effectively inhibit vagal response occurrence during subsequent RF applications by increasing the basal heart rate.³⁶ RF lines will be manually traced, aiming to avoid, if possible, the 'fingerprinted' image of the esophagus, projected on the LA posterior wall (see Appendix 4). Maximal interlesion distance will be 6 mm. VisiTag settings will be as follows: catheter position stability: minimum time 3 s, maximum range 4 mm; force over time: 25%, minimum force 3 g; lesion tag size: 3 mm. The irrigation flow rate must be set to 2 ml/min during mapping and 17-30 ml/min during ablation. AI targets are defined by local AWT on the thickness color map, as follows: Thickness < 1 mm (red): 300; 1-2 mm (yellow): 350; 2-3 mm (green): 400; 3-4 mm (blue): 450; > 4 mm (purple): 500. The recommended power settings to reach these AI values will be, in general, 35W for the posterior wall and 40W for the anterior wall. Wherever local AWT is > 3 mm (green and blue colors), an increased RF power (50W) will be permitted to reach the AI target faster, particularly if the catheter is placed in an unstable place. If the targeted AI value is not reached, another lesion reaching the target must be applied.

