3.6.2 Procedural evaluation

5. MDCT wall thickness variables
 - 5.1. Mean LAWV (all of the atrial measures)
 - 5.2. Mean PVI RF line WT (only around the PV line)
 - 5.3. Normalized PVI RF line WT (point thickness/maximum PVI RF line thickness)
 - 5.4. Reconnection point mean WT (mean thickness on a 3mm radius around the point)
 - 5.5. Reconnection segment mean WT (mean thickness in each segment)
 - 5.6. Coefficient of variation of wall thickness on each segment (CV-WT) standard deviation of the wall thickness/mean WT
 - 5.7. Gaussian curvature (to have an idea of the heterogeneity of tissue)
6. Procedural data of the first PVI
 - 6.1. PV anatomy (presence or absence of common vein ostia)
 - 6.2. RF time
 - 6.3. Acute reconnection sites
7. Procedural data of the re-do intervention
 - 7.1. Reconnection sites according to an 8-segment model where the antral region of the PVs is divided into segments
 - 7.2. RF time
 - 7.3. EGM attenuation time

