3.11 Statistical analysis

3.11.1 Sample size

The sample size calculation has been based on the assumption that the proposed ablation protocol ('LAWT') is an acceptable alternative to the CLOSE protocol¹⁵ (non-inferiority), with the advantage of less radiofrequency applied and likely lower risk for complications. A non-inferiority margin of 10% of clinical success (arrhythmia-free survival one year after the ablation procedure) will be considered to be the largest difference that is acceptable

between both protocols for LAWT to be adopted in clinical practice. Recruiting $n = 106$ participants will be required to confer 90% power to reject the inferiority null hypothesis, that is, that the lower limit of a one-sided 95% confidence interval will be above the non-inferiority limit of -0.05 , indicating no difference between the arms. A drop-out rate of 10% is estimated, and included in the sample size calculation.

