3.11.2 Statistical methods

All applicable statistical tests will be 2-sided and will be performed using a 5% significance level. Continuous variables will be reported as mean \pm standard deviation, or median (range or interquartile range if data are skewed) if not normally distributed; these variables will be compared using Student's t-test if normally distributed or Mann-Whitney U test if not normally distributed. Categorical variables will be expressed as total number (percentage) and will be compared by chi-squared test. For the primary endpoint, survival free from atrial arrhythmia, we will use the Kaplan-Meier survival analysis. A multivariable Cox proportional hazards model will be performed to investigate the effects of baseline characteristics in predicting ablation results, an adjustment will also be done by recruiting center. A receiver operating curve analysis will be performed to determine optimal cutoff LAWT values for predicting AF recurrence after ablation. All efforts will be done to limit missing data on outcome. Nevertheless, missing data will be reported on the final manuscript and, as much as possible, the reasons why data are missing will be documented. If missing, a simple imputation method will be applied and reported.

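### The planned ROC cutoff for left atrial wall thickness would rest on about 8–9 recurrences, too few to give a usable threshold; report an exploratory AUC with its confidence interval instead

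*Combined protocol and SAP*

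**What the plan says.** Section 3.11.2 (Statistical methods) lists a Kaplan-Meier analysis for the primary endpoint and a Cox model on baseline characteristics, adjusted for centre. It then adds: "A receiver operating curve analysis will be performed to determine optimal cutoff LAWT values for predicting AF recurrence after ablation". It does not say which thickness measure enters the ROC, how the optimum is defined, whether the cutoff will carry a confidence interval, whether it will be internally validated, or whether the analysis is exploratory. Section 3.6.2 offers several thickness measures, among them a whole-atrium mean, a mean along the isolation line (item 5.2) and segment means.

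Three other places bear on the point. Section 1 reports that in CLOSE "91.3% of the patients free from AF/AT/atrial flutter (AFL) at 12 months follow-up". Section 3.11.1 sets n = 106 and adds: "A drop-out rate of 10% is estimated, and included in the sample size calculation". Section 3.4.3 ties the dose to thickness: "AI targets are defined by local AWT on the thickness color map, as follows", running from 300 below 1 mm to 500 above 4 mm.

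**The concern.** An optimal cutoff is picked by searching all observed values for the one that best splits recurrent from non-recurrent patients. With few recurrences, each one moves sensitivity by a large step (one in eight is 12.5 points), so the chosen value follows chance. The sensitivity and specificity quoted at that value are inflated, because the same patients were used to choose it. The search also always returns a value, whether or not thickness predicts anything.

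At stake is a published thickness threshold in millimetres that looks precise and would probably not be reproduced in a second cohort.

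**Working it through.** **Plan's own figure.** The documents give no event count for the ROC, so there is none to reproduce. N = 106 is taken as stated. Section 3.11.1 does not give the success rate behind it. Using 91.3%, a 10-point margin, one-sided 5% and 90% power in a one-sample test, n = (1.645 × √(0.813 × 0.187) + 1.282 × √(0.913 × 0.087))² / 0.10² ≈ 101, or 101 / 0.9 → 113 with drop-out. That does not match 106 exactly, but the event count needs only N and a recurrence rate.

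**Expected recurrences.** Inputs: N = 106 and 10% drop-out (3.11.1); 91.3% success (section 1).
- Evaluable: 106 × 0.9 = 95.4, about 95.
- Recurrence rate: 1 − 0.913 = 0.087.
- Events: 95 × 0.087 = 8.3; 106 × 0.087 = 9.2. The 95% binomial range is 3–14 for n = 95.
- Ten points worse than CLOSE: 95 × 0.187 = 17.8; 106 × 0.187 = 19.8, about 20.

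**Precision of the AUC (Hanley-McNeil).** With A = 0.70, a = A/(2 − A) = 0.538 and b = 2A²/(1 + A) = 0.576. Then SE² = [A(1 − A) + (n₁ − 1)(a − A²) + (n₀ − 1)(b − A²)] / (n₁n₀).
- 8 v 87: (0.21 + 7 × 0.0485 + 86 × 0.0865) / 696 = 0.01147; SE = 0.107; 95% CI 0.49–0.91.
- 20 v 86: SE = 0.070; 95% CI 0.56–0.84.

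**True optimum for a true AUC of 0.70.** Under equal-variance normal thickness, the groups differ by √2 × Φ⁻¹(0.70) = 0.74 SD. The Youden optimum lies halfway, at 0.37 SD, and Φ(0.37) = 0.64, the 64th percentile of non-recurrent patients. True J = 2 × 0.6446 − 1 = 0.29.

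**Stability of the estimated cutoff.** Simulation, 20,000 runs, Youden criterion:

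| Events / patients | True AUC | Selected cutoff, 5–95% of runs (percentile of non-recurrent) | Apparent J | True J |
|---|---|---|---|---|
| 8 / 95 | 0.70 | about 33rd to 92nd–93rd | 0.44 | 0.29 |
| 20 / 106 | 0.70 | about 38th to 88th | – | 0.29 |
| 8 / 95 | 0.50 | no true optimum exists | 0.20 (median) | 0 |

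In the no-association case J reaches at least 0.30 in about 22% of runs. A separate 5,000-run simulation gives that case a 95% range for the chosen cutoff of −1.95 to 1.89 SD, which is nearly the whole spread of thickness. The same simulation, with 19 events in 95 and a true AUC of 0.70, gives an average apparent J of 0.39 against the true 0.29.

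**The case against.** **The ROC is a side analysis.** It serves no objective in section 2.2 and no endpoint in section 3.5, and nothing in the primary analysis depends on it. That stands, and it keeps the point minor.

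**The recurrence count may be higher than 8–9.** Section 3.5.1 also counts recurrences reported by symptoms alone. That is possible, but the 20-event row shows that roughly doubling the count still leaves the cutoff spread over half the distribution.

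**The no-association result is not dramatic.** With no true link, about 78% of runs stay below J = 0.30, so most null results would look weak. That is fair. The stronger evidence is the spread and optimism when a real association exists.

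**A reader might go further and infer that dosing by thickness makes the ROC invalid.** The argument would be that section 1 says "AI/wall thickness indexes have demonstrated to predict gaps on PVI lines", that target AI per millimetre falls as the wall thickens, and that the ROC, having no dose term, therefore cannot tell thickness from dose. The documents do not support that as a defect. The stated purpose is prediction, and no section says the cutoff will be used to reset AI targets or to claim a causal thickness effect. The near-perfect rank correlation one can compute between thickness and target AI per millimetre (−0.99) comes largely from dividing by thickness. A constant AI at every point gives −1.00. With delivered AI scattered around target by an assumed SD of 50, a constant AI gives −0.91 to −0.96 and the protocol's table −0.83 to −0.89, so the adapted table slightly weakens the link. What remains is a limit on interpretation: any association describes prediction under this dosing table.

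**A reader might also infer the same gap in the objective on failed first-pass isolation.** That is a separate question with its own planned data source. The sheet in Appendix 2 has the operator mark each segment where first pass failed and give the reason.

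**Conclusion.** The concern holds for the cutoff. With 8–9 expected recurrences, the planned step would give a thickness threshold whose position is largely chance and whose apparent accuracy is inflated by about half (J of 0.44 against 0.29). An AUC remains legitimate as a description of prediction under the protocol's AI targets, although its interval would be wide (0.49–0.91 at an observed 0.70).

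The sizes rest on the CLOSE rate carrying over, on 95 evaluable patients, on equal-variance normal thickness, and on the Youden criterion. The last two are assumptions, since the plan specifies neither. The conclusion is not sensitive to the event rate up to about 20 recurrences. Severity is minor: N, the primary endpoint and its analysis do not change.

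**What to change.** In section 3.11.2, replace the ROC sentence with: 'The AUC of mean PVI RF line WT (item 5.2) for AF recurrence will be reported with a 95% CI as an exploratory analysis; it applies only under the thickness-based AI targets in 3.4.3. No optimal cutoff will be derived.'

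Item 5.2 is suggested because it measures the tissue that is actually ablated. Another measure would do, provided one is named in advance.

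If the sponsor wants to keep a cutoff, state the criterion, give the cutoff a bootstrap confidence interval, report optimism-corrected sensitivity and specificity, and label it exploratory. The correction belongs with the cutoff; for the AUC of a single prespecified marker it changes essentially nothing.

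In either case the report should say that an association is not evidence of a thickness effect independent of dose.

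Cost: one sentence, with no new data, visits or patients. The downside is that the report loses a headline thickness cutoff.

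### An unnamed simple imputation of missing outcomes is not reconciled with Kaplan-Meier, and at 10% drop-out the value imputed can move the estimate by about the 10-point margin

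*Combined protocol and SAP*

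**What the plan says.** Section 3.11.2 sets the primary analysis: "For the primary endpoint, survival free from atrial arrhythmia, we will use the Kaplan-Meier survival analysis". Later in the same section the plan turns to incomplete outcomes. It first says "All efforts will be done to limit missing data on outcome", promises to report missing data with reasons where possible, and closes with "If missing, a simple imputation method will be applied and reported". The order of the sentences ties the imputation to outcome data. The section does not name the method, the value to be imputed, a missingness assumption or a sensitivity analysis. It also does not say whether a patient lost to follow-up is censored or imputed.

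Section 3.11.1 supplies the decision rule and the scale of the loss. Non-inferiority requires that "the lower limit of a one-sided 95% confidence interval will be above the non-inferiority limit", and on drop-out: "A drop-out rate of 10% is estimated, and included in the sample size calculation". Section 3.1 makes the study single-arm, so there is no concurrent group in which the same imputation could offset itself.

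**The concern.** Kaplan-Meier already has a rule for incomplete follow-up: the patient is censored. Adding a single imputation to the same outcome gives two rules for one patient, and the plan does not say which governs.

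The two rules differ in effect. Single imputation enters a filled value as if it had been observed, so the interval is computed on more patients than supplied data. In a single-arm comparison with a benchmark, the imputed value also moves the estimate directly. The planned drop-out (10% of patients) is as large as the stated margin (10 points), so the choice of value could settle the primary conclusion.

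**Working it through.** **Inputs**
- N = 106, 90% power, one-sided 95% limit, 10% drop-out: section 3.11.1.
- Benchmark 91.3% arrhythmia-free at 12 months: section 1, the CLOSE study. Using it as a fixed comparator is my assumption; section 3.11.1 states no rate.
- Margin 10 points: section 3.11.1, which then gives the limit as -0.05. That contradiction must be reconciled separately. I use 10 points here and show -0.05 at the end.
- Test level one-sided 5%, as in section 3.11.1. Section 3.11.2 instead says "All applicable statistical tests will be 2-sided and will be performed using a 5% significance level".
- Missing: 10% of 106 = 10.6, taken as 11 patients with no outcome, leaving 95. This is an assumption.
- Binomial outcome as an approximation to Kaplan-Meier.

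**The plan's own figure.** The 106 cannot be rebuilt exactly, because no expected success rate is stated. With 91.3%, a 10-point margin, one-sided 5%, 90% power and division by 0.9, N is 77 (Wald variance), 110 (arcsine) or 113 (exact). With -0.05 it is 304 or more. So 106 is compatible with the 10-point margin and not with -0.05.

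**Pass thresholds.** Limit = 0.913 − 0.10 = 0.813.
- P(Bin(106, 0.813) ≥ 94) = 0.029 and P(≥ 93) = 0.052, so 94 of 106 are needed.
- Missing = success: 94 − 11 = 83 of the 95 observed.
- No imputation: 84 of 95, since P(Bin(95, 0.813) ≥ 84) = 0.044.
- Missing = failure: 94 of 95.

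**Chance of passing, by rule and true rate among observed patients**

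| Rule | Observed successes needed | True 81.3% | True 91.3% |
|---|---|---|---|
| Missing = success | ≥ 83/95 | 7.8% | 93% |
| No imputation | ≥ 84/95 | 4.4% | 88% |
| Missing = failure | ≥ 94/95 | almost 0 | 0.2% |

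**One data set under each rule.** Take 87/95 observed successes (91.6%), with exact one-sided 95% lower limits.
- Missing = success: 98/106 = 92.5%, limit 86.8%: passes.
- No imputation: 87/95 = 91.6%, limit 85.3%: passes.
- Missing = failure: 87/106 = 82.1%, limit 74.8%: fails.
- The estimate ranges over 92.5 − 82.1 = 10.4 points.
- Tipping point, with the rest of the 11 counted as successes: 4 failures gives 94/106, limit 82.3%, passes; 5 failures gives 93/106, limit 81.2%, fails.

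**Drop-outs doing worse than the rest.** Suppose 50% success among the missing (an illustrative assumption) and 81.3% overall. The observed rate is (106 × 0.813 − 11 × 0.50)/95 = 0.849. Then P(Bin(95, 0.849) ≥ 83) = 31% with missing = success, and P(≥ 84) = 21% with no imputation.

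**If the limit is -0.05 instead.** Limit = 0.913 − 0.05 = 0.863. The exact test then needs 98 of 106, more than the 95 observed, so missing = failure can never pass. With 87/95 observed, missing = success passes (86.8%) and no imputation fails (85.3%) by the exact limit.

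**The case against.** The strongest reply is that this is a gap in wording with extremes attached. Several parts of it stand.

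- A reader might infer that any simple imputation favours the claim. The documents do not support that, because no rule is named. Success-type rules raise the error rate; failure-type rules push it towards zero and work against the sponsor.
- A reader might infer that carrying forward an arrhythmia-free visit is what reverses the result. At the 10-point margin, with 87/95 observed, it does not: success-imputation and no imputation both pass, and the reversal needs 5 or more of the 11 counted as failures. Nor do the documents say that carry-forward is intended.
- A reader might attribute the 31% to imputation. Most of it comes from the assumed informative drop-out, which gives 21% with no imputation.
- A reader might infer that the method will be picked after the data are seen. The plan says only that it will be reported, not when it is chosen.
- The 11 fully missing outcomes may be too many. Section 3.7 schedules visits at 3, 6 and 12 months, so some lost patients will have partial follow-up, and a recurrence before loss already counts. Part of the 10% could also be cases excluded under sections 3.4.3 and 3.10.3, which would not be imputed.
- Kaplan-Meier censoring might absorb every loss and leave nothing to impute for the primary estimate.

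The last reply does not close the point, because the plan does not say so. As written, the sentence applies imputation to missing outcomes, and both extreme rules fall within it.

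**Conclusion.** The concern holds in this form: an unnamed single imputation is applied to missing outcomes and is not reconciled with Kaplan-Meier. The value chosen can move the estimate by about the whole 10-point margin, and the chance of passing at the benchmark rate can lie anywhere from 0.2% to 93%, with 88% if nothing is imputed. For success-type rules only, the error rate at the limit is 7.8% against 4.4% for the observed patients alone.

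These figures show that the rule can decide the claim, not that it will. They rest on the fixed 91.3% benchmark, the 10-point margin, 11 patients with no outcome and a binomial stand-in for Kaplan-Meier. The gap in the text is certain; the sizes are conditional. Censoring is the better primary rule because it does not count unobserved outcomes as data, but it assumes non-informative loss, so a sensitivity analysis is needed beside it.

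**What to change.** Delete the simple-imputation sentence for the primary endpoint in section 3.11.2 and write instead:

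> Primary analysis: Kaplan-Meier with censoring at the last rhythm assessment, no imputation. Sensitivity analysis: a tipping-point table giving the number of missing patients counted as failures at which the conclusion changes.

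Multiple imputation from baseline covariates and follow-up to the last visit is optional. The tipping-point table needs one agreed limit, so the 10% and -0.05 statements in section 3.11.1 must be reconciled first.

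The cost is a change of wording and a short extra programme, with no added patients or visits. The downside is a slightly wider interval: at equal rates, a standard error on 95 rather than 106 patients is larger by √(106/95) = 1.056, about 6%.
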